10.4 Post-Treatment Follow-Up

Assessments for subjects who have completed durvalumab and tremelimumab treatment and achieved disease control, or have discontinued durvalumab or tremelimumab due to toxicity in the absence of confirmed progressive disease are provided in Appendix 2.

Assessments for subjects who have discontinued durvalumab or tremelimumab treatment due to confirmed PD are presented in Appendix 3.

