Grade 3	Hold study drug/study regimen until resolution to \leq Grade 1 or baseline. For AEs that downgrade to \leq Grade 2 within 7 days or resolve to \leq Grade 1 or baseline within 14 days, resume study drug/study regimen administration. Otherwise, discontinue study drug/study regimen.	Treat accordingly, as per institutional standard.
Grade 4	Discontinue study drug/study regimen (Note: For Grade 4 labs, decision to discontinue should be based on accompanying clinical signs/symptoms, the Investigator's clinical judgment, and consultation with the Sponsor.).	Treat accordingly, as per institutional standard.

Note: As applicable, for early phase studies, the following sentence may be added: "Any event greater than or equal to Grade 2, please discuss with Study Physician."

AE Adverse event; CTCAE Common Terminology Criteria for Adverse Events; NCI National Cancer Institute.

Appendix 2

Schedule of study procedures: follow-up for subjects who have completed durvalumab and tremelimumab treatment and achieved disease control (no confirmed progression of disease) or subjects who have discontinued durvalumab or tremelimumab due to toxicity in the absence of confirmed progression of disease

Evaluation	Time Since Last Dose of Durvalumab
------------	------------------------------------

	Day (± 3)	Months (± 1 week)					12 Months and (± 2 weeks)	Every 6 Months	
		30	2	3	4	6	8	10	
Full physical examination	X		X	X					
Vital signs (temperature, respiratory rate, blood pressure, pulse)	X								
Oxygen saturation (pulse oximetry)	X								
Weight	X								
Urine hCG or serum β hCG	X								
AE/SAE assessment ^{a, b}	X		X	X					
Concomitant medications ^a	X		X	X					
Palliative radiotherapy	As clinically indicated					→			
ECOG performance status	X		X	X	At time points consistent with tumor assessments until loss of clinical benefit				
Subsequent anti-cancer therapy ^a	X		X	X	X	X	X	X	
Survival status ^a				X	X	X	X	X	(every 2 months)
CBC	X		X	X					
Serum chemistry	X		X	X					
Research blood tests	A total of 2 additional research blood draws after the first 3 research blood draws may be performed at the discretion of the study physician								
Thyroid function tests (TSH, and fT3 and fT4 if TSH is abnormal) ^c	X		X	X					

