Tumour assessment (CT or MRI)	
For subjects who achieve disease control following 48 weeks of treatment, tumour assessments should be performed every 12 weeks (+/- 14 days) relative to the date of first infusion thereafter until confirmed PD by RECIST 1.1 by investigational site review. Please refer to section 10 and 12 for timings of confirmatory scans.
 
For subjects who discontinue treatment due to toxicity (or symptomatic deterioration), tumour assessments should be performed relative to the date of first infusion as follows: every 8 weeks for the first 48 weeks, then every 12 weeks until confirmed PD by RECIST 1.1 by investigational site review. Please refer to Section 10 and 12 for timings of confirmatory scans.
								

^a Can be collected by phone.

^b Patients with ongoing \geq grade 2 or serious AEs will continue to be followed until the event is resolved to baseline or deemed irreversible or clinically insignificant by the site investigator, or start of new therapy.

^c Free T3 and free T4 will only be measured if TSH is abnormal or if there is clinical suspicion of an endocrine related AE.

Appendix 3

Schedule of study procedures: follow-up for subjects who have discontinued durvalumab and tremelimumab treatment due loss of clinical benefit at the investigator discretion

Evaluation	Time Since Last Dose of durvalumab							
	Day (± 3)	Months (± 1 week)						12 Months and Every 6 Months (± 2 weeks)
	30	2	3	4	6	8	10	
Full physical examination	X							
Vital signs (temperature, respiratory rate, blood pressure, pulse)	X							
Oxygen saturation (pulse oximetry)	X							
Weight	X							
AE/SAE assessment ^{a,b}	X	X	X					
Concomitant medications ^a	X							
Palliative radiotherapy	As clinically indicated							
ECOG performance status	X							
Subsequent anti-cancer therapy ^a	X	X	X	X	X	X	X	
Survival status ^a		X	X	X	X	X	X	X (every 2 months)
Urine hCG or serum β hCG	X							
CBC	X							
Serum chemistry	X							
Thyroid function tests (TSH, and fT3 and fT4 if TSH is abnormal) ^c	X							
Pharmacokinetic assessment, if applicable								
Research blood test	A total of 2 additional research blood draws after the first 3 research blood draws may be performed at the discretion of the study physician							

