Tumour assessment (CT or MRI)	For subjects who continue treatment post-confirmed progression at the investigator's discretion, tumour assessments should be performed relative to the date of first infusion per section 10 until durvalumab is stopped. For subjects who discontinue durvalumab following loss of clinical benefit , scans should be conducted according to local clinical practice and submitted for central review until a new treatment is started (these scans are optional).							

^a Can be collected by phone.

^b Patients with ongoing \geq grade 2 or serious AEs will continue to be followed until the event is resolved to baseline or deemed irreversible or clinically insignificant by the site investigator, or start of new therapy.

^c Free T3 and free T4 will only be measured if TSH is abnormal or if there is clinical suspicion of an endocrine related AE.

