^a If a CR is truly met at the first timepoint, any disease seen at a subsequent timepoint, even disease meeting PR criteria relative to baseline, qualifies as PD at that point (since disease must have reappeared after CR). Best response would depend on whether the minimum duration for SD was met. However, sometimes CR may be claimed when subsequent scans suggest small lesions were likely still present and in fact the patient had PR, not CR, at the first timepoint. Under these circumstances, the original CR should be changed to PR and the best response is PR.

C. Special Notes on Response Assessment

When nodal disease is included in the sum of target lesions and the nodes decrease to “normal” size (<10 mm), they may still have a measurement reported on scans. This measurement should be recorded even though the nodes are normal in order not to overstate progression should it be based on increase in size of the nodes. As noted earlier, this means that patients with CR may not have a total sum of “zero” on the CRF.

Patients with a global deterioration of health status requiring discontinuation of treatment without objective evidence of disease progression at that time should be reported as “symptomatic deterioration.” Every effort should be made to document objective progression even after

discontinuation of treatment. Symptomatic deterioration is not a descriptor of an objective response; it is a reason for stopping study therapy. The objective response status of such patients is to be determined by evaluation of target and non-target disease as shown in Tables 1–3.

For equivocal findings of progression (e.g., very small and uncertain new lesions; cystic changes or necrosis in existing lesions), treatment may continue until the next scheduled assessment. If at the next scheduled assessment progression is confirmed, the date of progression should be the earlier date when progression was suspected.

In studies for which patients with advanced disease are eligible (i.e., primary disease still or partially present), the primary tumor should also be captured as a target or non-target lesion, as appropriate. This is to avoid an incorrect assessment of complete response if the primary tumor is still present but not evaluated as a target or non-target lesion.

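### A patient who stops for clinical deterioration without RECIST progression fits both post-treatment scan schedules or neither, and one schedule makes scans optional, which can bias PFS upward

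*Combined protocol and SAP*

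**What the plan says.** **Appendix 2.** The title covers patients who completed treatment with disease control, and "subjects who have discontinued durvalumab or tremelimumab due to toxicity in the absence of confirmed progression of disease". It does not mention symptomatic deterioration, but the tumour-assessment row does: "For subjects who discontinue treatment due to toxicity (or symptomatic deterioration), tumour assessments should be performed relative to the date of first infusion", at an interval of "every 8 weeks for the first 48 weeks, then every 12 weeks until confirmed PD by RECIST 1.1 by investigational site review".

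**Appendix 3.** The title reads "follow-up for subjects who have discontinued durvalumab and tremelimumab treatment due loss of clinical benefit at the investigator discretion". It does not ask for RECIST progression. For patients who stop after loss of clinical benefit, the tumour-assessment row says "scans should be conducted according to local clinical practice and submitted for central review until a new treatment is started (these scans are optional".

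**Sections 9.4 and 10.4.** Section 10.4 states: "Assessments for subjects who have discontinued durvalumab or tremelimumab treatment due to confirmed PD are presented in Appendix 3". Section 9.4 says the same. Both give Appendix 2 to patients with disease control after completing treatment and to patients who stop for toxicity without confirmed progression. Neither mentions stopping for clinical deterioration.

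**Section 9.4, end-of-treatment visit.** A disease assessment is implied, since a repeat is waived only if one was done in the preceding 28 days. The procedures may be skipped, with permission, if the patient is unfit or unwilling to attend.

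**Section 14.3.** PFS events are recurrence, progression or death, with censoring at the last follow-up date. The median and the 24-week rate (plus or minus 1 week) are reported. DOR runs from confirmed response to progression or death.

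**Appendix 4.** Symptomatic deterioration is treated as a reason for stopping therapy, not as a response category. The text adds "Every effort should be made to document objective progression even after" treatment has been discontinued.

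**The concern.** The plan expects patients of this kind. Section 9.2 ties the end of treatment to lack of clinical benefit rather than to RECIST progression, and the response-evaluable definition in section 14.2 provides for withdrawal because of clinical progression before any post-baseline scan.

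For these patients the scan schedule depends on which appendix the site opens. Under Appendix 2, progression is looked for at fixed intervals. Under Appendix 3 it may not be looked for at all. Survival is still followed (section 13.1), and both appendices allow survival status to be collected by phone. With censoring at last follow-up rather than at last scan, an unscanned patient keeps gaining progression-free time until death or last contact.

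The missing scans would fall in patients who are already declining, so the error in PFS runs upward. DOR ends on the same events and has the same weakness for any responder who stops this way.

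**Working it through.** **1. The plan's own figure.** The documents give no expected value for PFS or DOR. The only design figure is the two-stage response rule: 13 then 14 patients, continue on at least 1 response, success on at least 4 of 27, with rates of 5% and 20%.

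P(success | p) = sum over x = 1 to 13 of P(Bin(13, p) = x) × P(Bin(14, p) ≥ 4 − x)

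- p = 0.05: 0.0416, within the 5% limit.
- p = 0.20: 0.8011, meeting 80% power.
- Early stop under 5%: 0.95^13 = 0.513.

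The design reproduces, and the scan conflict does not enter it. Patients withdrawn for clinical progression before a post-baseline scan stay in the response-evaluable set, in effect as non-responders.

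**2. Where the patient is placed.** Take a patient who stops for clinical deterioration with no RECIST progression on record.

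| Text | Covers this patient? | Scans |
|---|---|---|
| Appendix 2, title | No | – |
| Appendix 2, scan row | Yes, by name | 8-weekly to week 48, then 12-weekly, until confirmed progression |
| Appendix 3, title and scan row | Yes, as loss of clinical benefit | Optional, local practice, until new treatment |
| 9.4 and 10.4, route to Appendix 2 | No | – |
| 9.4 and 10.4, route to Appendix 3 | No (confirmed progression only) | – |

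The appendices' scan rows give two answers and the body text gives none.

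**3. Effect per patient.** With 27 patients and no earlier censoring, the Kaplan-Meier rate at week 24 is a simple proportion. One patient whose progression before week 24 goes unrecorded, and who is alive and in contact at week 24, moves it by 1/27 = 3.7 points. This is a maximum: the shift is smaller if last contact comes earlier.

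Assumption, not in the documents: 3 to 5 of 27 patients stop this way, about half are alive at week 24, and none is scanned again.

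- 3 × 0.5 = 1.5 patients; 1.5/27 = 5.6 points.
- 5 × 0.5 = 2.5 patients; 2.5/27 = 9.3 points.

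**4. Cross-check by simulation.** All inputs are assumed. Times are exponential, and the medians are those in the table. Progression is seen at the next scan (8-weekly to week 48, then 12-weekly) unless death comes first. In a fraction f of patients, drawn at random, progression is never seen and the event is death. Entries are the percentage event-free beyond week 25, the upper edge of the 24-week window.

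| Median months to progression / from progression to death | f = 0 | 10% | 20% | 30% |
|---|---|---|---|---|
| 2 / 4 | 14.6 | 19.1 | 23.8 | 28.4 |
| 2 / 8 | 14.8 | 20.9 | 27.2 | 33.2 |
| 3 / 4 | 27.8 | 31.8 | 36.0 | 40.0 |
| 3 / 8 | 28.0 | 33.3 | 38.7 | 43.8 |
| 4 / 8 | 38.4 | 43.2 | 47.5 | 52.4 |

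The rise is about 4 to 6 points at 10%, 8 to 12 at 20% and 12 to 18 at 30%. Three to five of 27 is 11% to 19%, so the 10% and 20% columns are the ones to compare with step 3, and they agree in size. In the 3/8 setting at 20%, median PFS moves from 16 to about 24 weeks.

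**The case against.** The best defence is that the documents can be read together. Appendix 2's scan row is the only text that names symptomatic deterioration. Sections 9.4 and 10.4 send only confirmed progression to Appendix 3, whose scan row opens with patients treated beyond confirmed progression. Sections 9.2 and 13.1 use clinical benefit as the test for continuing past RECIST progression. On that reading Appendix 3 is the post-progression schedule and its heading is merely loose.

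This is plausible, but the text does not force it. Appendix 3's heading requires no progression, Appendix 2's title omits deterioration, and 9.4 and 10.4 do not place the patient. The end-of-treatment assessment and the Appendix 4 instruction also help, but the first can be skipped for the patients least fit to attend, and neither sets a continuing schedule.

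Some stronger readings do not hold:

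- **Appendix 2 makes 8-weekly scans mandatory.** It says they should be performed, and the interval lengthens to 12 weeks after week 48.
- **Section 10.3 is a further defect.** It governs imaging during treatment and stops at lack of clinical benefit, as treatment does; 10.4 governs what follows.
- **These progressions are simply lost.** Death is an event, so many are recorded late. Only patients alive at last contact escape altogether.
- **Censoring at the last scan would leave a bias of 5 to 8 points.** That figure treats all 3 to 5 patients as censored. If deaths count as events, 1.5 to 2.5 are censored. With assumed survival of 60% at censoring and 25% at week 24, the credit is 0.25/0.60 = 0.42 each, giving 1.5 × 0.42/27 = 2.3 to 2.5 × 0.42/27 = 3.9 points. In any case the plan censors at last follow-up.
- **DOR is shown to be inflated.** It could be, but it concerns responders only, and nothing in the documents allows the effect to be sized.

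**Conclusion.** The inconsistency stands in the current text. A patient who stops for deterioration without RECIST progression has two conflicting scan schedules in the appendices and no assignment in sections 9.4 and 10.4. If the optional schedule is used, PFS is biased upward, and DOR potentially so.

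The only size that follows from the documents is the ceiling of 3.7 points per patient on the 24-week PFS rate. The 6 to 9 points rest on an assumed 1.5 to 2.5 patients wrongly carried as progression-free, and the simulated 4 to 18 points on an assumed 10% to 30% of progressions missed. Neither is a forecast.

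A reader might infer that the trial's main conclusion is at risk. It is not. The response rule is not materially affected, and PFS and DOR are single-arm descriptive summaries with no test attached. The point should be corrected, but it does not undermine the design. It is worth settling before follow-up because scans that were never taken cannot be recovered in the analysis.

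**What to change.** Reconcile Appendix 2, Appendix 3, section 9.4 and section 10.4 so that endpoint imaging after treatment is routed by RECIST status rather than by the reason for stopping:

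- Patients without documented RECIST 1.1 progression at end of treatment follow the Appendix 2 tumour-assessment schedule.
- Appendix 3's optional scans apply only after RECIST 1.1 progression has been documented.
- The two appendix titles and the cross-references in 9.4 and 10.4 use the same definition.

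This concerns only the collection of endpoint data; it does not alter when treatment stops.

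Optionally, add a PFS sensitivity analysis that counts stopping for symptomatic deterioration as an event, to cover patients who cannot be scanned.

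The cost is a wording amendment and a few more scans, which Appendix 2's row already specifies for these patients. Some will be too unwell to attend, so the gap will narrow rather than close.

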Appendix 4 The Response Evaluation Criteria in Solid Tumors (RECIST 1.1)

Modified Excerpt from Original Publication

Selected sections from the Response Evaluation Criteria in Solid Tumors (RECIST), Version 1.1¹ are presented below, with slight modifications and the addition of explanatory text as needed for clarity.²

I. Measurability of Tumor at Baseline

Definitions

At baseline, tumor lesions/lymph nodes will be categorized measurable or non-measurable as follows:

A. Measurable Tumor Lesions

Tumor Lesions. Tumor lesions must be accurately measured in at least one dimension (longest diameter in the plane of measurement is to be recorded) with a minimum size of:

- 10 mm by CT or MRI scan (CT/MRI scan slice thickness/interval no greater than 5 mm)
- 10-mm caliper measurement by clinical examination (lesions that cannot be accurately measured with calipers should be recorded as non-measurable)
- 20 mm by chest X-ray

Malignant Lymph Nodes. To be considered pathologically enlarged and measurable, a lymph node must be ≥ 15 mm in the short axis when assessed by CT scan (CT scan slice thickness recommended to be no greater than 5 mm). At baseline and in follow-up, only the short axis will be measured and followed. See also notes below on “Baseline Documentation of Target and Non-Target Lesions” for information on lymph node measurement.

B. Non-Measurable Tumor Lesions

Non-measurable tumor lesions encompass small lesions (longest diameter < 10 mm or pathological lymph nodes with ≥ 10 to < 15 mm short axis), as well as truly non-measurable lesions. Lesions considered truly non-measurable include: leptomeningeal disease, ascites, pleural or pericardial effusion, inflammatory breast disease, lymphangitic involvement of skin or lung, peritoneal spread,

¹ Eisenhauer EA, Therasse P, Bogaerts J, et al. New response evaluation criteria in solid tumors: Revised

² RECIST guideline (Version 1.1). Eur J Cancer 2009;45:228–47.

For consistency within this document, the section numbers and cross-references to other sections within the article have been deleted and minor formatting changes have been made.

and abdominal masses/abdominal organomegaly identified by physical examination that is not measurable by reproducible imaging techniques.

C. Special Considerations Regarding Lesion Measurability

Bone lesions, cystic lesions, and lesions previously treated with local therapy require particular comment, as outlined below.

Bone lesions: Bone scan, positron emission tomography (PET) scan, or plain films are not considered adequate imaging techniques to measure bone lesions. However, these techniques can be used to confirm the presence or disappearance of bone lesions.

- Lytic bone lesions or mixed lytic-blastic lesions, with identifiable soft tissue components, that can be evaluated by cross-sectional imaging techniques such as CT or MRI can be considered measurable lesions if the soft tissue component meets the definition of measurability described above.
- Blastic bone lesions are non-measurable.

Cystic lesions: Lesions that meet the criteria for radiographically defined simple cysts should not be considered malignant lesions (neither measurable nor non-measurable) since they are, by definition, simple cysts.

- Cystic lesions thought to represent cystic metastases can be considered measurable lesions if they meet the definition of measurability described above. However, if non-cystic lesions are present in the same patient, these are preferred for selection as target lesions.

Lesions with prior local treatment: Tumor lesions situated in a previously irradiated area, or in an area subjected to other loco-regional therapy, are usually not considered measurable unless there has been demonstrated progression in the lesion. Study protocols should detail the conditions under which such lesions would be considered measurable.

II. Target Lesions: Specifications by Methods of Measurements

A. Measurement of Lesions

All measurements should be recorded in metric notation, using calipers if clinically assessed. All baseline evaluations should be performed as close as possible to the treatment start and never more than 4 weeks before the beginning of the treatment.

B. Method of Assessment

The same method of assessment and the same technique should be used to characterize each identified and reported lesion at baseline and during study. Imaging-based evaluation should always be the preferred option.

Clinical Lesions. Clinical lesions will only be considered measurable when they are superficial and ≥ 10 mm in diameter as assessed using calipers (e.g., skin nodules). For the case of skin lesions, documentation by color photography, including a ruler to estimate the size of the lesion, is suggested.

Chest X-Ray. Chest CT is preferred over chest X-ray, particularly when progression is an important endpoint, since CT is more sensitive than X-ray, particularly in identifying new lesions. However, lesions on chest X-ray may be considered measurable if they are clearly defined and surrounded by aerated lung.

CT, MRI. CT is the best currently available and reproducible method to measure lesions selected for response assessment. This guideline has defined measurability of lesions on CT scan based on the assumption that CT slice thickness is 5 mm or less. When CT scans have slice thickness greater than 5 mm, the minimum size for a measurable lesion should be twice the slice thickness. MRI is also acceptable.

If prior to enrollment it is known that a patient is unable to undergo CT scans with intravenous (IV) contrast due to allergy or renal insufficiency, the decision as to whether a non-contrast CT or MRI (without IV contrast) will be used to evaluate the patient at baseline and during the study should be guided by the tumor type under investigation and the anatomic location of the disease. For patients who develop contraindications to contrast after baseline contrast CT is done, the decision as to whether non-contrast CT or MRI (enhanced or non-enhanced) will be performed should also be based on the tumor type and the anatomic location of the disease and should be optimized to allow for comparison with the prior studies if possible. Each case should be discussed with the radiologist to determine if substitution of these other approaches is possible and, if not, the patient should be considered not evaluable from that point forward. Care must be taken in measurement of target lesions on a different modality and interpretation of non-target disease or new lesions since the same lesion may appear to have a different size using a new modality.

Ultrasound. Ultrasound is not useful in assessment of lesion size and should not be used as a method of measurement.

Endoscopy, Laparoscopy, Tumor Markers, Cytology, Histology. The utilization of these techniques for objective tumor evaluation cannot generally be advised.

III. Tumor Response Evaluation

A. Assessment of Overall Tumor Burden and Measurable Disease

To assess objective response or future progression, it is necessary to estimate the overall tumor burden at baseline and to use this as a comparator for subsequent measurements. Measurable disease is defined by the presence of at least one measurable lesion, as detailed above.

B. Baseline Documentation of Target and Non-Target Lesions

When more than one measurable lesion is present at baseline, all lesions up to a maximum of five lesions total (and a maximum of two lesions per organ) representative of all involved organs should be identified as target lesions and will be recorded and measured at baseline. This means in instances where patients have only one or two organ sites involved, a maximum of two lesions (one site) and four lesions (two sites), respectively, will be recorded. Other lesions (albeit measurable) in those organs will be recorded as non-measurable lesions (even if the size is > 10 mm by CT scan).

Target lesions should be selected on the basis of their size (lesions with the longest diameter) and be representative of all involved organs, but additionally, should lend themselves to reproducible repeated measurements. It may be the case that, on occasion, the largest lesion does not lend itself to reproducible measurement, in which circumstance the next largest lesion that can be measured reproducibly should be selected.

Lymph nodes merit special mention since they are normal anatomical structures that may be visible by imaging even if not involved by tumor. As noted above, pathological nodes that are defined as measurable and may be identified as target lesions must meet the criterion of a short axis of ≥ 15 mm by CT scan. Only the short axis of these nodes will contribute to the baseline sum. The short axis of the node is the diameter normally used by radiologists to judge if a node is involved by solid tumor. Nodal size is normally reported as two dimensions in the plane in which the image is obtained (for CT scan, this is almost always the axial plane; for MRI the plane of acquisition may be axial, sagittal, or coronal). The smaller of these measures is the short axis. For example, an abdominal node that is reported as being $20\text{ mm} \times 30\text{ mm}$ has a short axis of 20 mm and qualifies as a malignant, measurable node. In this example, 20 mm should be recorded as the node measurement. All other pathological nodes (those with short axis ≥ 10 mm but < 15 mm) should be considered non-target lesions. Nodes that have a short axis < 10 mm are considered non-pathological and should not be recorded or followed.

A sum of the diameters (longest for non-nodal lesions, short axis for nodal lesions) for all target lesions will be calculated and reported as the baseline sum of diameters. If lymph nodes are to be included in the sum, then, as noted above, only the short axis is added into the sum. The baseline

sum of diameters will be used as a reference to further characterize any objective tumor regression in the measurable dimension of the disease.

All other lesions (or sites of disease), including pathological lymph nodes, should be identified as non-target lesions and should also be recorded at baseline. Measurements are not required and these lesions should be followed as “present,” “absent,” or in rare cases “unequivocal progression.”

In addition, it is possible to record multiple non-target lesions involving the same organ as a single item on the Case Report Form (CRF) (e.g., “multiple enlarged pelvic lymph nodes” or “multiple liver metastases”).

IV. Response Criteria

A. Evaluation of Target Lesions

This section provides the definitions of the criteria used to determine objective tumor response for target lesions.

- **Complete response (CR):** disappearance of all target lesions. Any pathological lymph nodes (whether target or non-target) must have reduction in short axis to < 10 mm.
- **Partial response (PR):** at least a 30% decrease in the sum of diameters of target lesions, taking as reference the baseline sum of diameters
- **Progressive disease (PD):** at least a 20% increase in the sum of diameters of target lesions, taking as reference the smallest sum on study (nadir), including baseline

In addition to the relative increase of 20%, the sum must also demonstrate an absolute increase of at least 5 mm.

The appearance of one or more new lesions is also considered progression.

Stable disease (SD): neither sufficient shrinkage to qualify for PR nor sufficient increase to qualify for PD, taking as reference the smallest sum on study.

B. Special Notes on the Assessment of Target Lesions

Lymph Nodes. Lymph nodes identified as target lesions should always have the actual short axis measurement recorded (measured in the same anatomical plane as the baseline examination), even if the nodes regress to <10 mm on study. This means that when lymph nodes are included as target lesions, the sum of lesions may not be zero even if CR criteria are met since a normal lymph node is defined as having a short axis <10 mm.

Target Lesions That Become Too Small to Measure. While on study, all lesions (nodal and non-nodal) recorded at baseline should have their actual measurements recorded at each subsequent evaluation, even when very small (e.g., 2 mm). However, sometimes lesions or lymph nodes that are recorded as target lesions at baseline become so faint on CT scan that the radiologist may not feel comfortable assigning an exact measure and may report them as being too small to measure. When this occurs, it is important that a value be recorded on the CRF as follows:

- If it is the opinion of the radiologist that the lesion has likely disappeared, the measurement should be recorded as 0 mm.
- If the lesion is believed to be present and is faintly seen but too small to measure, a default value of 5 mm should be assigned and BML (below measurable limit) should be ticked.
(Note: It is less likely that this rule will be used for lymph nodes since they usually have a definable size when normal and are frequently surrounded by fat such as in the retroperitoneum; however, if a lymph node is believed to be present and is faintly seen but too small to measure, a default value of 5 mm should be assigned in this circumstance as well and BML should also be ticked.)

To reiterate, however, if the radiologist is able to provide an actual measure, that should be recorded, even if it is below 5 mm, and, in that case, BML should not be ticked.

Lesions That Split or Coalesce on Treatment. When non-nodal lesions fragment, the longest diameters of the fragmented portions should be added together to calculate the target lesion sum. Similarly, as lesions coalesce, a plane between them may be maintained that would aid in obtaining maximal diameter measurements of each individual lesion. If the lesions have truly coalesced such that they are no longer separable, the vector of the longest diameter in this instance should be the maximal longest diameter for the coalesced lesion.

C. Evaluation of Non-Target Lesions

This section provides the definitions of the criteria used to determine the tumor response for the group of non-target lesions. While some non-target lesions may actually be measurable, they need not be measured and, instead, should be assessed only qualitatively at the timepoints specified in the protocol.

- **Complete Response (CR):** disappearance of all non-target lesions and (if applicable) normalization of tumor marker level)

All lymph nodes must be non-pathological in size (<10 mm short axis).
- **Non-CR/Non-PD:** persistence of one or more non-target lesion(s) and/or (if applicable) maintenance of tumor marker level above the normal limits

- **Progressive Disease (PD):** unequivocal progression of existing non-target lesions. The appearance of one or more new lesions is also considered progression.
-

D. Special Notes on Assessment of Progression of Non-Target Disease

When the Patient Also Has Measurable Disease. In this setting, to achieve unequivocal progression on the basis of the non-target disease, there must be an overall level of substantial worsening in non-target disease in a magnitude that, even in the presence of SD or PR in target disease, the overall tumor burden has increased sufficiently to merit discontinuation of therapy. A modest increase in the size of one or more non-target lesions is usually not sufficient to qualify for unequivocal progression status. The designation of overall progression solely on the basis of change in non-target disease in the face of SD or PR of target disease will therefore be extremely rare.

When the Patient Has Only Non-Measurable Disease. This circumstance arises in some Phase III trials when it is not a criterion of study entry to have measurable disease. The same general concepts apply here as noted above; however, in this instance, there is no measurable disease assessment to factor into the interpretation of an increase in non-measurable disease burden. Because worsening in non-target disease cannot be easily quantified (by definition: if all lesions are truly non-measurable), a useful test that can be applied when assessing patients for unequivocal progression is to consider if the increase in overall disease burden based on the change in non-measurable disease is comparable in magnitude to the increase that would be required to declare PD for measurable disease, that is, an increase in tumor burden representing an additional 73% increase in volume (which is equivalent to a 20% increase in diameter in a measurable lesion). Examples include an increase in a pleural effusion from “trace” to “large” or an increase in lymphangitic disease from localized to widespread or may be described in protocols as “sufficient to require a change in therapy.” If unequivocal progression is seen, the patient should be considered to have had overall PD at that point. While it would be ideal to have objective criteria to apply to non-measurable disease, the very nature of that disease makes it impossible to do so; therefore, the increase must be substantial.

E. New Lesions

The appearance of new malignant lesions denotes disease progression; therefore, some comments on detection of new lesions are important. There are no specific criteria for the identification of new radiographic lesions; however, the finding of a new lesion should be unequivocal, that is, not attributable to differences in scanning technique, change in imaging modality, or findings thought to represent something other than tumor (for example, some “new” bone lesions may be simply healing or flare of pre-existing lesions). This is particularly important when the patient’s baseline lesions

show partial or complete response. For example, necrosis of a liver lesion may be reported on a CT scan report as a “new” cystic lesion, which it is not.

A lesion identified during the study in an anatomical location that was not scanned at baseline is considered a new lesion and will indicate disease progression.

If a new lesion is equivocal, for example because of its small size, continued therapy and follow-up evaluation will clarify if it represents truly new disease. If repeat scans confirm there is definitely a new lesion, then progression should be declared using the date of the initial scan.

V. Evaluation of Response

A. Timepoint Response (Overall Response)

It is assumed that at each protocol-specified timepoint, a response assessment occurs. Table 1 provides a summary of the overall response status calculation at each timepoint for patients who have measurable disease at baseline.

When patients have non-measurable (therefore non-target) disease only, Table 2 is to be used.

Table 1.

Timepoint Response : Patients with Target Lesions (with or without Non-Target Lesions)

Target Lesions	Non-Target Lesions	New Lesions	Overall Response
CR	CR	No	CR
CR	Non-CR/non-PD	No	PR
CR	Not evaluated	No	PR
PR	Non-PD or not all evaluated	No	PR
SD	Non-PD or not all evaluated	No	SD
Not all evaluated	Non-PD	No	NE
PD	Any	Yes or no	PD
Any	PD	Yes or no	PD
Any	Any	Yes	PD

CR=complete response; NE = not evaluable; PD=progressive disease; PR=partial response;
SD=stable disease.

Table 2. Timepoint Response: Patients with Non-Target Lesions Only

Non-Target Lesions	New Lesions	Overall Response
CR	No	CR
Non-CR/non-PD	No	Non-CR/non-PD ^a
Not all evaluated	No	NE
Unequivocal PD	Yes or no	PD
Any	Yes	PD

CR = complete response; NE = not evaluable; PD = progressive disease.

